5.0 ENROLLMENT

The patients at the top of the adult kidney transplant list awaiting DDKT maintained by UIHHSS Transplant will be used to screen for eligibility. See addendum for Eligibility Checklist. Study personnel will perform the screening. A password protected Microsoft Excel sheet will be provided by the Transplant team at UIHHSS. This sheet will have the MRN for the top patients on the kidney transplant list. If patients are initially eligible via inclusion and exclusion review, they will remain on the password protected Microsoft Excel sheet. If they are not eligible, they will be removed after screening by one of the study personnel. This password protected Microsoft Excel sheet will be maintained on the "H" drive behind the University firewall maintained by the CCTS. It is estimated that 40 subjects will be consented/enrolled in order for 20 patients to receive study drug. Twenty patients are the goal for this study and no more than 20 patients will receive study drug.

All eligible study subjects will receive a Research Letter (see addendum for Research Letter) via the mail. One week after the Research Letter is mailed, the subjects that have not called the primary investigator regarding the study will be called via telephone by study personnel to follow-up and provide any additional information regarding the study. This call is to provide information regarding the study, study enrollment criteria, and answer any questions regarding the study. This call is informational only.

If a kidney transplant is offered to the previously contacted subjects the study personnel will be contacted by the Transplant Coordinator when the kidney transplant is confirmed. Once that subject arrives at UI Health for their transplant, subjects will be approached by study investigators in-person, reminded of the study criteria, have ample time to review study information again and the informed consent document, and will be asked to provide signed consent after the appropriate informed consent process is completed. Researchers participating in the consent process will review the informed consent document (ICD) with the recruited subject in its entirety ensuring the subject understands the research purpose, all risks/benefits and the study components of this research.

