Patients will be monitored according to standard monitoring for patients in the peri-operative transplant and collection of ADE will focus on those found in clinical studies using Ang II (Giapreza). The safety endpoints that will be captured will include: incidence of intraoperative arrhythmias for those who receive study drug intraoperatively (confirmed via EKG, flowsheet, or note documentation), incidence of postoperative arrhythmias occurring while receiving study drug postoperatively (confirmed via EKG, flowsheet, or note documentation), incidence of digital or other peripheral/visceral ischemia occurring during hospitalization for kidney transplant (as noted in chart documentation), incidence of venous or arterial thrombosis occurring during the hospitalization for kidney transplant (captured by ultrasound or other diagnostic imaging), incidence of thrombocytopenia while receiving study drug (as defined as platelet count < 50,000), incidence of post-operative fungal infections prior to discharge (as documented by the clinical care team), incidence of delirium while receiving study drug (as documented by the clinical care team), incidence of insulin infusion utilization while receiving study drug, pH values in the ICU at 24hrs, 48hrs, and 72hrs (if available). All of the noted safety variables above are routinely monitored for as part of ICU care.

Data Management

All patients that provide informed consent and receive Ang II (Giapreza) will have their data extracted. These patients will be considered included and associated with an alpha-numeric code that is linked to their medical record number (MRN). This list will be kept in a password protected Excel file on the primary investigator's computer stored on the H drive behind the University firewall on the primary investigator's password protected computer in a locked office. It will be available only to the co-investigators. Lastly, all data collected will not contain PHI and will be stored in Redcap.

All patients that provide informed consent but DO NOT receive Ang II (Giapreza) will be considered a screening failure and NO data will be extracted and they will not be associated with an alpha-numeric code linked to their MRN.

Records retention:

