8.0 DATA COLLECTION AND MANAGEMENT PROCEDURES

Subjects will be screened for eligibility by the study personnel. The investigators will review a list of kidney transplant patients maintained by the Transplant Coordinators for inclusion in the study. This list will be password protected and stored on the H drive behind the University firewall on the primary investigator's password protected computer in a locked office. If a subject is not eligible after reviewing inclusion and exclusion criteria, they will be removed from this list. All subjects that provide informed consent to receive Ang II (Giapreza) will remain on this list. If a subject is enrolled and receives Ang II (Giapreza), their de-identified data will be extracted and collected in Redcap. Additionally, they will be associated with an alpha-numeric code that is linked to their medical record number (MRN) and placed on a Study Subject list. This Study Subject list will be kept in a password protected Excel file on the primary investigator's computer stored on the H drive behind the University firewall on the primary investigator's password protected computer in a locked office. It will be available only to the coinvestigators and research personnel. If a subject is enrolled and does not require Ang II (Giapreza) they will be considered a screening failure and their de-identified data will NOT be extracted or collected and their MRN will NOT be placed on the Study Subject list. All data points collected will be de-identified, containing no PHI and will be stored in Redcap. All study personnel will have access to the Redcap database.

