10.0 QUALITY CONTROL AND QUALITY ASSURANCE

All personnel collecting data will be taught where to obtain the most accurate information from Cerner and Epic to capture the desired data points. After the first subject of the pilot is enrolled and discharged from the institution, data collected will be audited by the primary and co-investigators. Two additional audits will occur: one after 5 subjects collected and one after 10 subjects collected. If these audits reveal any discrepancies, additional audits will be performed on an as needed basis.

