Probably Related: An event that follows a reasonable temporal sequence from administration of the Ang II and there is a biologically plausible mechanism for Ang II (Giapreza) to cause or contribute to the AE and the event could not be reasonably explained by the known characteristics of the participant's clinical state.

For reporting purposes, both 'Possibly Related' and 'Probably Related' will be considered **Related**.

Adverse events will also be graded by severity according to CTCAE criteria.

- -Grade 1: Mild; Asymptomatic or mild symptoms; clinical or diagnostic observations only; intervention not indicated.
- -Grade 2: Moderate; Minimal, local or noninvasive intervention indicated; limiting age-appropriate instrumental activities of daily living.
- -Grade 3: Severe; Medically significant but not immediately life-threatening; hospitalization or prolongation of hospitalization indicated; disabling; limiting self-care activities of daily living.
- -Grade 4: Life-threatening consequences; urgent intervention indicated.
- -Grade 5: Death related to AE.

Given this is a clinical trial a Data Safety Monitoring Board (DSMB) will be established. This board will be composed of two Critical Care Pharmacists ([name] and [name]) with intimate knowledge of Ang II (Giapreza), vasopressors, Ang II (Giapreza) safety endpoints and no relationship to the conduct of the trial. This DSMB will review the safety endpoints collected above after 5, 10, 15, and 20 subjects are enrolled. They will be provided a Safety Summary Report for the allotted number of patients with "Relatedness" and Grading of captured ADE as described above.

Study Halting Criteria: For existing participants study drug will halt dosing immediately until further safety analysis and assessment by the DSMB can be completed and no further enrollment will take place until approved by the DSMB. The halting criteria are as follows:

- Two participants experience the same Grade 4 adverse event considered related to study drug
- 20% of the participants at time of analysis experience the same Grade 3 adverse event
- One participant experiences a Grade 5 AE considered related to study drug

Study can be restarted if the DSMB says it is okay to continue.

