13.0 REGULATORY REQUIREMENTS

13.1 INFORMED CONSENT

The patients at the top of the adult kidney transplant list awaiting DDKT maintained by UIHHSS Transplant will be used to screen for eligibility. See addendum for Eligibility Checklist. Study personnel will perform the screening. A password protected Microsoft Excel sheet will be provided by the Transplant team at UIHHSS. This sheet will have the MRN for the top patients on the kidney transplant list. If patients are initially eligible via inclusion and exclusion review, they will remain on the password protected Microsoft Excel sheet. If they are not eligible, they will be removed after screening by one of the study personnel. This password protected Microsoft Excel sheet will be maintained on the "H" drive behind the University firewall maintained by the CCTS. It is estimated that patients

will be required to be screened assuming a consent rate of ~50% and vasopressor utilization rate of ~50% of patients that receive a deceased donor kidney transplant. It is estimated that 40 subjects will be consented/enrolled in order for 20 patients to receive study drug. Twenty patients are the goal for this study and no more than 20 patients will receive study drug.

All eligible study subjects will receive a Research Letter (see addendum for Research Letter via the mail. One week after the Research Letter is mailed, the subjects will be called via telephone by study personnel to follow-up and provide any additional information regarding the study. This call is to provide information regarding the study, study enrollment criteria, and answer any questions regarding the study. This call is informational only.

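### The DSMB review schedule counts subjects enrolled, a word the protocol elsewhere applies to consented but undosed subjects, so read literally the last review falls at about 10 of 20 treated patients

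*Combined protocol and SAP*

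**What the plan says.** The schedule in section 11.0 reads: "This DSMB will review the safety endpoints collected above after 5, 10, 15, and 20 subjects are enrolled". No later DSMB review is scheduled. One of the three halting criteria in the same section depends on a proportion: "20% of the participants at time of analysis experience the same Grade 3 adverse event". The other two act on events: a second instance of the same related Grade 4 event, or one related Grade 5 event.

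Three other sections show who counts as enrolled:

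- Section 5.0, repeated in 13.1: "It is estimated that 40 subjects will be consented/enrolled in order for 20 patients to receive study drug". Enrolled is paired with consented and set against receiving drug.
- Section 8.0: "If a subject is enrolled and does not require Ang II (Giapreza) they will be considered a screening failure". A subject can be enrolled and never dosed.
- Section 13.1 gives the planning rate behind the 40: "vasopressor utilization rate of ~50% of patients that receive a deceased donor kidney transplant".

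For dosed patients the protocol has other terms. Under Data Management in section 6.0, of those who consent and receive the drug: "These patients will be considered included and associated with an alpha-numeric code". The later audits in section 10.0 are timed as "one after 5 subjects collected and one after 10 subjects collected".

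**The concern.** If the trigger means what enrolled means in sections 5.0, 8.0 and 13.1, the reviews use up their four slots while only about half of the planned patients have been treated. The Grade 3 criterion is judged at the time of an analysis, and after the 20th consent none is scheduled. A Grade 3 pattern that builds up in later patients would then have no scheduled route to the DSMB.

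This matters more than usual here. The background section says that no data exist on this drug in renal transplant patients, and under section 11.0 the researchers themselves judge relatedness. The DSMB members are the safety reviewers described as having no part in running the trial. Staff who book meetings by the written trigger would comply with the protocol and still leave the later patients outside the schedule.

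**Working it through.** **Inputs.** Reviews at 5, 10, 15 and 20 enrolled (section 11.0); vasopressor use of about 50% among transplanted patients (13.1); at most 20 dosed (5.0); halting at 20% with the same Grade 3 event (11.0). The documents give no Grade 3 rate, so 10%, 20% and 30% are assumed.

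**1. The plan's own figure.** Enrolled needed = dosed / vasopressor use = 20 / 0.50 = 40. This agrees with section 5.0 and confirms that enrolled there includes undosed subjects.

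**2. Dosed patients at each review, read literally.** The number dosed among n enrolled is Binomial(n, 0.5), with mean 0.5n.

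| Enrolled | Mean dosed | 90% range |
|---|---|---|
| 5 | 2.5 | 1–4 |
| 10 | 5 | 2–8 |
| 15 | 7.5 | 4–11 |
| 20 | 10 | 6–14 |

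The chance that the first review has at most one dosed patient is (1 + 5)/32 = 18.75%.

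**3. Patients dosed after the last scheduled review.** 20 − Binomial(20, p). At p = 0.5 the mean is 20 − 10 = 10 (90% range 6 to 14). Over an assumed range of p, the mean is 20 − 8 = 12 at 40% use and 20 − 12 = 8 at 60% use.

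**4. Chance that the Grade 3 criterion is met at a scheduled review.** Simulation with 400,000 replicates, 20 dosed patients, independent events and p = 0.5. The denominator is dosed patients in both columns.

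- Reviews by dosed count: met if at least 1 of 5, 2 of 10 or 3 of 15 have the event. The review at 20 dosed is left out because no one remains to be dosed.
- Reviews by enrolled count: met if events/dosed is at least 20% at 5, 10, 15 or 20 enrolled.

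| Assumed rate | Reviews at 5, 10, 15 dosed | Reviews at 5, 10, 15, 20 enrolled |
|---|---|---|
| 10% | 48% | 40% |
| 20% | 80% | 70% |
| 30% | 94% | 87% |

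**5. Missed patterns.** Take the trials that end with at least 4 of 20 dosed patients affected, at a 20% rate. The criterion is never met at a review that could still stop dosing in 4.4% with reviews at 5, 10 and 15 dosed, and in 14.5% with reviews by enrolled count. The difference is about 10 percentage points.

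**The case against.** The strongest reply is that the intent is plain and a sensible team would count treated patients. Four points support it, and all four stand:

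- The sentence after the schedule promises the DSMB a summary report for the allotted number of patients. Undosed subjects cannot fill such a report, because those who "DO NOT receive Ang II (Giapreza) will be considered a screening failure and NO data will be extracted".
- The schedule ends at 20, which is the dosing cap in section 5.0 and the study size in section 6.0.
- Usage is mixed. Section 10.0 times its first audit from a subject who is enrolled and discharged. Data exist only for dosed patients, so that subject must have been dosed.
- Fluid-refractory shock needing a vasopressor is itself an inclusion criterion in section 4.1.

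These show what was probably meant. They do not define the trigger, and sections 5.0, 8.0 and 13.1 are explicit in the other direction.

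A reader might go further and infer that the 20% criterion is diluted by counting undosed subjects among the participants. The documents give little support for that. Undosed subjects are screening failures, and the halting paragraph speaks of participants in connection with stopping their dosing. The word should be tied down, but no effect size should be claimed for that scenario.

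A reader might also infer that the second half of the treated patients has no protection. That is not so. The related Grade 4 and Grade 5 halts do not wait for a review, the treating physician may stop the drug at once (section 6.0), and unforeseen concerns go to the IRB (section 13.3). Nor is the time of analysis defined as a scheduled DSMB review, so the lapse of the Grade 3 criterion after the last review is an inference, though a natural one.

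**Conclusion.** The point holds as a wording defect in a stated safety rule, probably contrary to its intent. The documents do not support saying that the sponsor plans to leave half the treated patients unreviewed. They support saying that the trigger as written permits it.

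Read literally, about 10 of 20 treated patients (90% range 6 to 14) fall after the last scheduled review. This rests on the protocol's 50% vasopressor use and on each consented subject needing a vasopressor independently. The loss in detection is modest: about 10 percentage points at an assumed 20% Grade 3 rate, with the same direction at 10% and 30%. Those figures assume independent events and a treated-patient denominator. The correction is worth making because it is nearly free and concerns safety oversight of a drug untested in this population.

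**What to change.** Make two changes in section 11.0.

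1. In the review schedule, replace *are enrolled* with *have received study drug*.
2. In the Grade 3 criterion, define the denominator as participants who have received study drug at the time of analysis.

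No new data are needed. The reviews would then fall at about 10, 20, 30 and 40 consented (5, 10, 15 and 20 divided by 0.50), and the last would cover all 20 treated patients.

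There is a trade-off against the literal schedule. The first review comes at 5 dosed rather than about 2 to 3. Reviews that can still stop dosing go from four to three, since the fourth comes after everyone is dosed. In return, patients dosed after the last review that can stop dosing fall from about 10 to 20 − 15 = 5. If an early look matters to the sponsor, one can be added after the second or third dosed patient.

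### The 20% halting rule names Grade 3 only, so at the 5-subject look one Grade 3 event pauses the study but one related event first graded 4 does not

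*Combined protocol and SAP*

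**What the plan says.** Section 11.0 gives three study halting criteria. Meeting any one stops dosing and enrollment until the DSMB has assessed the data.

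- Grade 4: "Two participants experience the same Grade 4 adverse event considered related to study drug".
- Grade 3: "20% of the participants at time of analysis experience the same Grade 3 adverse event". There is no condition on relatedness.
- Grade 5: one related event is enough.

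The same section separates the grades. Grade 3 is "Medically significant but not immediately life-threatening"; Grade 4 is "Life-threatening consequences; urgent intervention indicated". On timing: "This DSMB will review the safety endpoints collected above after 5, 10, 15, and 20 subjects are enrolled". A halt is a pause: "Study can be restarted if the DSMB says it is okay to continue". Section 5.0 caps exposure: "Twenty patients are the goal for this study and no more than 20 patients will receive study drug".

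Nothing in the document says that the 20% criterion covers Grade 3 and above, or that a single Grade 4 event halts the study.

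**The concern.** Halting criteria should need fewer events as severity rises. Here a percentage is used for Grade 3 and a fixed count for Grade 4, and the percentage is confined to one grade. An event first graded 4 therefore drops out of the 20% count that it would have entered had it been milder. When the denominator is 5, one Grade 3 event reaches 20%, while one related Grade 4 event meets no criterion. The difference in attribution widens the gap, because the Grade 3 event need not be related to the drug.

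Section 2 says there are no data on this drug in kidney transplant patients, and these criteria are the only pre-set quantitative guard at study level. The order of severity fails at the first look, when least is known.

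**Working it through.** The plan states no operating characteristics for its halting rules, so there is no figure of its own to reproduce.

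**Inputs from Section 11.0.** Looks at n = 5, 10, 15 and 20; Grade 3 threshold 20% of participants; Grade 4 threshold 2 related events of the same type. I read 20% as 20% or more.

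**Step 1: events needed to halt.** The Grade 3 count is 0.20 × n; the Grade 4 count is always 2.

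| Look | Grade 3 events | Related Grade 4 events | Mix reaching 20% that meets no criterion |
|---|---|---|---|
| 5 | 1 | 2 | 0 Grade 3 + 1 related Grade 4 |
| 10 | 2 | 2 | 1 + 1 |
| 15 | 3 | 2 | 2 + 1 |
| 20 | 4 | 2 | 3 + 1 |

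The single-event inversion occurs only at the 5-subject look. The mixes at 10 and 15 matter only if no earlier look halted the study. The mix at 20 has almost no practical effect if looks count dosed patients, because dosing is then complete.

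**Step 2: chance of a halt at the first look.** The rates are assumptions. For one event type, let p3 be the Grade 3 rate, p4 the related Grade 4 rate and q = 1 − p3 − p4. Each participant is counted once, at one grade, and looks count dosed patients.

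- As written, there is no halt if nobody has Grade 3 and at most one has related Grade 4: P(halt) = 1 − [q⁵ + 5·p4·q⁴].
- If related Grade 4 events also count: P(halt) = 1 − q⁵.

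Take a 10% total rate with one fifth related Grade 4 (p3 = 0.08, p4 = 0.02, q = 0.90). As written: 1 − [0.5905 + 5 × 0.02 × 0.6561] = 0.344. With the change: 1 − 0.5905 = 0.410.

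| Total severe rate | As written, 20% of events related Grade 4 | As written, 50% | With the change |
|---|---|---|---|
| 5% | 19% | 12% | 23% |
| 10% | 34% | 25% | 41% |
| 20% | 59% | 47% | 67% |

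Sections 5.0 and 13.1 expect 40 enrolled for 20 dosed. If looks count enrolled subjects and half are dosed, the effective rate per subject halves, and the 10% row becomes 19% / 12% against 23%.

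**Step 3: cumulative chance.** Here the rules are applied in sequence at 5, 10 and 15, with counts carried forward and each event known by the look that closes its block of five. At a 10% total rate, the chance of a halt by the 15-subject look is 41% / 38% as written (20% / 50% related Grade 4) and 48% / 50% with the change.

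**The case against.** The strongest reply is that the DSMB is already reviewing when the gap opens. If the time of analysis means the scheduled looks, a related Grade 4 event among the first five is before the board at that moment: "They will be provided a Safety Summary Report for the allotted number of patients with" relatedness and grade. A formal halt would refer the event to the same board. This stands in part. The event is not hidden, and the loss is limited to the mandatory stop in dosing and enrollment while the board deliberates. No written rule requires that stop, and the physician's right in Section 6.0 to discontinue the drug does not pause the study.

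Second, the inversion is confined to one look, and from 15 subjects on the Grade 4 criterion needs fewer events than the Grade 3 one. That is correct. The inability to pool grades remains at 10 and 15 but needs a particular mix of events.

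Third, the case depends on readings. If 20% meant strictly more than 20%, two Grade 3 events would be needed at n = 5 and the single-event inversion would vanish. That is not the plain reading, and one Grade 3 plus one related Grade 4 of the same event (2/5 = 40%) would still not halt. An event that passes through Grade 3 before worsening may already count; the protocol does not say whether only the highest grade is used.

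Fourth, the rates are assumed, and the model cannot separate warranted from unwarranted pauses. With eight independent event types, each at a 10% rate, a first-look halt is already 97% / 90% likely as written (1 − 0.656⁸ and 1 − 0.754⁸), against 98.5% with the change. So at high rates across many event types the change adds little at study level. The logical defect does not depend on the rates.

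Fifth, Sections 7.0 and 11.0 describe label dosing and low expected risk. This bears on how often the gap would matter, not on whether the rule is correctly ordered.

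**Conclusion.** The concern holds. Followed exactly, the criteria let a milder and possibly unrelated event force a pause at the 5-subject look that a related life-threatening event does not. This follows from the text and needs only the plain reading of 20% as 20% or more, with the event first graded 4.

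Its practical size is moderate. Under the assumed rates for one event type, the first-look chance of a pause is lower by 4 to 20 percentage points than if related Grade 4 events counted (smallest 23% against 19%, largest 67% against 47%). DSMB oversight limits the harm without restoring the automatic pause. It should be corrected before the first look.

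**What to change.** Reword the second criterion in Section 11.0 along these lines: *at the time of analysis, 20% or more of participants have had the same type of event either at Grade 3, whatever its attribution, or at Grade 4 or above with a related attribution.* Leave the other two criteria unchanged. This closes the gap for related events, including one that worsens from Grade 3 to Grade 4, and settles the meaning of 20%.

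It still leaves an unrelated Grade 4 event uncounted while an unrelated Grade 3 event counts. Extending the criterion simply to Grade 3 and above, with no relatedness condition, removes that too but brings more pauses. Requiring at least two participants under the Grade 3 rule would also remove the single-event inversion, but it would make the first look less sensitive and would not let grades be pooled.

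The cost is extra pauses. Chance of at least one over four looks, at assumed rates:

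| | 2% Grade 3, 1% related Grade 4 | 5% and 2% |
|---|---|---|
| One event type, as written | 11.5% | 29.6% |
| One type, related Grade 4 counted | 15.7% | 36.3% |
| One type, Grade 3 and above, unrelated Grade 4 at 1% / 2% / 4% | 20.6% / 25.5% / 35.1% | 40.8% / 45.3% / 53.8% |
| Eight independent types, as written | 62% | 94% |
| Eight types, related Grade 4 counted | 74% | 97% |
| Eight types, Grade 3 and above, unrelated Grade 4 at 2% | 90% | 99% |

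The eight-type rows use 1 − (1 − p)⁸; eight is about the number of safety endpoints listed in Section 11.0. The change needs no extra patients, procedures or staff. The choice between the two wordings belongs to the sponsor and the DSMB.

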Subjects can withdraw from the study at any time. This withdrawal will not impact any portion of their care other than not being able to receive the study drug as it is not formulary approved at our institution. If a patient withdraws, their data will not be collected or used for analysis. Confidentiality will be maintained by using password protection for the Excel sheets, password protection for the computers used for storage of those Excel sheets, storing the sheet on the University H firewall behind the firewall and storing de-identified data within Redcap.

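### The withdrawal rule discards all data from any patient who withdraws, including treated patients and outcomes already recorded, and does not fit the data-extraction rules in sections 6.0 and 8.0

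*Combined protocol and SAP*

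**What the plan says.** Section 11.0 (data and safety monitoring) deals with withdrawal in three sentences. The first sets no time limit: "Subjects can withdraw from the study at any time". The second describes the consequence for care: "This withdrawal will not impact any portion of their care other than not being able to receive the study drug". The third is the data rule: "If a patient withdraws, their data will not be collected or used for analysis".

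Two other sections say whose data are gathered. Under Data Management in section 6.0: "All patients that provide informed consent and receive Ang II (Giapreza) will have their data extracted". In section 8.0: "If a subject is enrolled and receives Ang II (Giapreza), their de-identified data will be extracted and collected in Redcap". Once consent has been given, the only exclusion in those two sections is for patients who never receive the drug. Neither mentions withdrawal or refers to section 11.0, and no section defines an analysis population.

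Two further provisions bear on the consequences. Section 5.0 caps treatment: "Twenty patients are the goal for this study and no more than 20 patients will receive study drug". Section 11.0 gives the DSMB a summary with relatedness and "Grading of captured ADE as described above", and one of its halting criteria is "20% of the participants at time of analysis experience the same Grade 3 adverse event".

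**The concern.** A treated patient who withdraws is covered by two opposite instructions: extract the data (sections 6.0 and 8.0), and neither collect nor use them (section 11.0). The part of the section 11.0 rule about collection could be read as looking forward only. The part about use in the analysis cannot, because it reaches data already held.

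The exposure is not confined to the infusion. Section 6.0 plans renal function at 1 and 3 months, a calcineurin inhibitor level at 6 months and renal replacement therapy through the first year. Read literally, a patient who withdraws during that follow-up also loses the perioperative record. That record holds time to BP goal, which is the primary objective, and the in-hospital safety endpoints.

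This is exclusion after treatment, for a reason that may be related to outcome. If patients with adverse events withdraw more often than others, reported incidence is too low. If patients who missed the BP goal withdraw more often, apparent effectiveness is too high. In a study of at most 20 treated patients, one removal is visible in the result.

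**Working it through.** **The text, side by side**

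| Patient | Sections 6.0 and 8.0 | Section 11.0 withdrawal rule |
|---|---|---|
| Consented, never dosed | No data | No data if withdrawn |
| Consented, dosed, stays in | Data extracted | Not applicable |
| Consented, dosed, withdraws | Data extracted | Data neither collected nor used |
| Drug stopped by the treating physician | Data extracted | Not described as withdrawal, so not at issue |

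Only the third row is in conflict.

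**The plan's own figure.** Sections 5.0 and 13.1 expect 40 consented patients to yield 20 treated. With the stated vasopressor use of about 50%, 20 / 0.50 = 40. The figure reproduces and is not in dispute. It contains no allowance for withdrawal.

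**Patients available for analysis.** The cap is on patients who receive drug, so a treated patient whose data are dropped has used one of the 20 places. With w such patients, at most 20 - w can be analysed.

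**Withdrawal rate.** The documents give none. If each of 20 treated patients withdrew independently with an assumed probability q, the chance of at least one withdrawal is 1 - (1 - q)^20: 64% at q = 5%, 88% at 10% and 99% at 20%. At q = 0 there is no effect.

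**Event incidence.** The intervals are exact (Clopper-Pearson) 95%. The lower limit solves P(X ≥ x) = 0.025 and the upper limit solves P(X ≤ x) = 0.025. One affected patient is dropped from 20 treated:

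- 4/20 = 20.0% (5.7 to 43.7) becomes 3/19 = 15.8% (3.4 to 39.6).
- 1/20 = 5.0% (0.1 to 24.9) becomes 0/19 = 0% (0 to 17.6).

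Dropping one unaffected patient moves incidence the other way: 4/20 becomes 4/19 = 21.1%, and 1/20 becomes 1/19 = 5.3%. If 1, 2, 3 or 4 affected patients are dropped from 4/20, the rate reads (4 - w)/(20 - w) = 15.8%, 11.1%, 5.9% or 0%.

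**Effectiveness.** Assume that 16 of 20 (80%) reach the BP goal. Dropping 1 to 4 patients who did not gives 16/19 = 84.2%, 16/18 = 88.9%, 16/17 = 94.1% or 16/16 = 100%.

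**Grade 3 halting criterion (at least 20%).** This applies only if the DSMB sees retained data alone. With treated denominators of 5, 10, 15 and 20, the criterion is just met at 1/5, 2/10, 3/15 and 4/20. Removing one affected patient gives 0/4 = 0%, 1/9 = 11.1%, 2/14 = 14.3% and 3/19 = 15.8%, so it is no longer met. A check of every count for 2 to 20 treated patients shows that other denominators behave differently:

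- Removing an affected patient can take the rate from above the threshold to below it, as in 2/7 = 28.6% to 1/6 = 16.7%. No such reversal occurs at 6, 11 or 16 treated.
- Removing an unaffected patient makes the criterion newly met only at those three sizes: 1/6 = 16.7% to 1/5 = 20.0%, 2/11 = 18.2% to 2/10 = 20.0%, and 3/16 = 18.8% to 3/15 = 20.0%.

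**The case against.** The best defence is that sections 6.0 and 8.0 are general record-handling rules that separate treated patients from screening failures, while section 11.0 holds the only rule on withdrawal. A specific rule beside a general one is ordinarily read as an exception. The sentence on losing access to study drug also suggests that the authors had withdrawal before or during treatment in mind. This has force: the exception reading may be the intended one. It does not remove the problem. Withdrawal during treatment is already withdrawal after dosing, the rule has no time limit, and an intended exception still discards treated patients.

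It can also be said that discarding the data may be a deliberate promise to participants. The consent form is not in the reviewed copy, so this cannot be excluded, and it must be checked before the rule is changed.

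Safety is partly handled elsewhere. Section 11.0 provides for assessment and reporting of adverse events, its halting criteria count participants who experience events, and section 13.3 sends unforeseen problems to the IRB. An event captured before withdrawal may therefore still count towards halting. None of these provisions puts the patient back into the analysis.

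The size is uncertain. The shift from 20.0% to 15.8% is small beside its intervals. DSMB reviews are timed by subjects enrolled, and section 5.0 uses that word for the 40 consented. On that reading about half of those enrolled at each review are treated, some 10 at the last scheduled one, so the 3/15 and 4/20 cases need not arise at a scheduled review. These limits stand. They bear on how much harm the rule would do, not on what it says.

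**Conclusion.** The concern holds and should be fixed. That the rule is unrestricted and, as written, removes treated patients who withdraw is clear from the text. Whether it contradicts sections 6.0 and 8.0 or is an exception nobody stated is less certain, and the consequence is the same.

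The certain cost is one analysable patient out of at most 20 for each treated patient who withdraws. A downward bias in adverse-event incidence rests on two assumptions that the documents do not settle: that some patients withdraw after dosing, and that those with events do so more often. Any effect on halting also depends on what the DSMB is shown and on the denominator, can go either way, and is held with low confidence.

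**What to change.** Reconcile the three sections by replacing the withdrawal sentence in section 11.0 with text to this effect: *When a patient withdraws, collection of new data ends on the withdrawal date. For each patient given any amount of Ang II, all data and adverse events recorded by that date are retained and enter the primary analysis, the safety analysis, the DSMB reports, and both the counts and the denominators of the halting criteria.*

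Report how many patients withdrew and when. State that a patient who withdraws before reaching the BP goal is censored at withdrawal in the time-to-goal analysis. It would also help to separate a patient who only declines further drug from one who refuses further data collection, so that follow-up a willing patient would allow is not lost. Check that the consent form agrees.

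The cost is one protocol paragraph through an IRB amendment, plus the consent check. Patients must be told that data already collected are kept. Events after withdrawal remain unobserved, so some downward bias can remain.
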